9.6.3 Additional Analyses

Not Applicable.

Confidentiality Statement

Philip Morris Products SA.	Statistical Analysis Plan	Confidential
P1-EXC-01-EU	Final 2.0	Page 53 of 71
Related to PMI-RRP-WKI-112487		SAP P1-EXC-01-EU

9.6.4 Safety Evaluation

9.6.4.1 Adverse Events

AEs (including SAEs) will be collected from the time of ICF signature until the EOS for all enrolled subjects. Information recorded will include: verbatim description of the AE/SAE, start and stop dates, seriousness, severity (intensity), relatedness (to IP and study procedures), expectedness, action taken (e.g., whether or not the AE/SAE led to the subject's withdrawal from the study), and outcome (e.g., resolved, stabilized).

Adverse events which occur during the screening period will be listed together with corresponding information.

Adverse events (AEs) will be coded using the MedDRA® dictionary.

A summary showing the overall number of AEs, SAEs, severity, expectedness, relatedness, AE leading to death, AE leading to action taken and treatment given for an AE will be presented.

The frequency of AEs and number (and percentage compared to total) of subjects for each AE will be determined within each study arm and for all study arms. This will be done for a given AE with respect to the system organ class (SOC) and preferred term according to MedDRA® will be determined within each study arm and for all study arms (total) and tabulated. Tabulation will be sorted by the decreasing frequencies within the system organ classes and preferred term (within the system organ class).

The frequencies of the severity (intensity) and relationship to study procedures and IP, expectedness, for each adverse event will be tabulated for each study arm by SOC and preferred term.

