### 2.3.2 Anticipated Foreseeable Risks due to Study Procedures

- Risks related to blood sampling (*e.g.*, excessive bleeding, fainting, hematoma, paresthesia or infection).
- Risk related to spirometry testing procedures (*e.g.*, dizziness or fainting). Administration of salbutamol for the spirometry testing may potentially elevate blood pressure, increase the heart rate and cause tremor, inner agitation, palpitation due to sinus tachycardia, muscle cramps or headaches. However, these effects are limited after single use and only more frequent following repeated use and oral administration.
- Risk related to VO2max test may include muscle cramps, muscle strain, delayed muscle soreness (1 to 2 days afterwards), light headedness, fatigue, and in rare instances, heart attack. These symptoms are expected physiological responses and are similar to what may occur if the subject undertakes a strenuous run or bike-ride by him- or herself.

Data and information contained in this document are considered to constitute trade secrets and confidential commercial information, and the legal protections provided to such trade secrets and confidential information are hereby claimed under the provisions of applicable law. No part of this document may be publicly disclosed without the written consent of Philip Morris Products S.A

Philip Morris Products SA	Clinical Study Protocol	Confidential
P1-EXC-01-EU	Version 3.0 / 2 May 2019	Page 35 of 151

• Risks related to exercise training include muscle cramps, muscle strain and delayed muscle soreness 1 to 2 days afterwards, fatigue. These symptoms are expected physiological responses and are similar to what may occur if the subject undertakes a strenuous run or bike-ride by him- or herself.

All risks related to study procedures will be explained in detail to the subjects. Mitigation will include:

- Using accepted research and scientific standards, (*e.g.*, blood samples not to exceed local blood donation standards).
- Before performing the first VO2max test at V1, subjects will undergo medical examinations and their medical history will be assessed. All exercise testing will be performed by trained study personnel and be medically supervised.
- Exercise training sessions will be supervised and performed on stationary bikes. During stationary bike ergometer exercise, the exerted loads on especially the knee joints and back will be smaller than during running exercise (42).

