### **Confidentiality Statement**

Philip Morris Products SA

Clinical Study Protocol

P1-EXC-01-EU

Version 3.0 / 2 May 2019

Confidential

Page 47 of 151

	Exclusion Criteria	Rationale	Screening	Enrollment V2
	neurological, hematological, endocrine, oncological, urological, immunological, pulmonary [such as but not limited to pulmonary oedema, asthma], and cardiovascular [such as, but not limited to myocardial infarction, unstable angina, uncontrolled arrhythmias, heart failure], disease) or any other clinically significant medical condition (including abnormal safety laboratory result as per CTCAE), which as per the judgment of the Investigator would jeopardize the safety of the subject.			
2.	Subject who has forced expiratory volume in 1 second/forced vital capacity (FEV 1 /FVC) <0.7 and FEV 1 <80% predicted value at post-bronchodilator spirometry (GOLD, 2017).	Safety	Х	
3.	Subject with asthma condition (FEV 1 /FVC < $0.75$ and reversibility in FEV 1 (in both > 12% and > 200 mL) from pre to post-bronchodilator values.	Safety	Х	
4.	Subject has clinical significant abnormalities of ECG at V1.	Safety	Х	
5.	Subject performs more than 45 min of vigorous physical activity per week.	Effect	Х	
6.	Inability to perform a VO₂max test at V1.	Safety	Х	
7.	VO 2 max >50 mL.min  kg  for men and VO 2 max >40 mL.min  kg  for women as determined at V1.	Effect	Х	
8.	Subject takes medication influencing blood volume such as erythropoietin, diuretics and beta blockers, or diabetic medications.	Effect	Х	
9.	Subject cannot participate in the study for any reason other than medical as per the Investigator's judgment (e.g. psychological and/or social reason)	Administrative	Х	
10.	For women only: subject is pregnant (does not have negative pregnancy tests at V1 and at V2) or is breastfeeding.	Safety	Х	x

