# 8.2.2 Period of Collection

AEs (including SAEs) will be collected from the time of ICF signature until the EOS.

Any AEs which occur during the screening period will be captured by the study site staff and assessed by the Investigator or designee(s) in order to establish relationship to study procedures.

Data and information contained in this document are considered to constitute trade secrets and confidential commercial information, and the legal protections provided to such trade secrets and confidential information are hereby claimed under the provisions of applicable law. No part of this document may be publicly disclosed without the written consent of Philip Morris Products S.A

Philip Morris Products SA	Clinical Study Protocol	Confidential
P1-EXC-01-EU	Version 3.0 / 2 May 2019	Page 75 of 151

During a 28-day safety follow-up period there will be recording of spontaneously reported new AEs/SAEs and the active follow-up of ongoing AEs/SAEs by the study site. In general, all AEs will be followed-up until resolved, stabilized (i.e., no worsening of the event), or a plausible explanation for the event has been found and until the end of the study. The follow-up of the ongoing non-serious AEs will be done via a phone call performed until the end of the Safety follow-up period. Any AEs or SAEs that are ongoing at the end of the safety follow-up period will be managed as described in Section 8.2.6.

SAEs spontaneously reported to the Investigator after the end of the safety follow-up period and considered related to the *IQOS* must also be reported to the Sponsor.

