# 8.4 Reporting and of Other Events Critical to Safety Evaluation

# 8.4.1 Abnormal Results of Laboratory Tests

Any clinical safety laboratory test result that is outside of the normal reference range will be reviewed by the Investigator and assessed for clinical significance according to its severity. The severity of abnormal laboratory test result must be assessed using CTCAE version 4.03 grading scales (Appendix 3).

Any clinical safety laboratory test result that is outside of the normal reference range will be reviewed by the Investigator and assessed for clinical significance according to its severity. Whenever that grading scheme is not available for the laboratory result of concern, the Investigator should assess the severity and the clinical significance of that result using his/her medical judgment.

Subjects with clinically significant abnormal laboratory values at Screening will not be enrolled. Abnormal laboratory test results detected at the Screening Visit whose CTCAE grades are 2 or higher or still are CTCAE grade 1 and deemed clinically significant are usually

Data and information contained in this document are considered to constitute trade secrets and confidential commercial information, and the legal protections provided to such trade secrets and confidential information are hereby claimed under the provisions of applicable law. No part of this document may be publicly disclosed without the written consent of Philip Morris Products S.A

Philip Morris Products SA	Clinical Study Protocol	Confidential
P1-EXC-01-EU	Version 3.0 / 2 May 2019	Page 78 of 151

concomitant disease or a manifestation of one and must be recorded accordingly. However, in some instances, they may be assessed as AEs (and therefore must be handled according to the directions in Section 8.2) or as manifestations of already reported AEs. This decision will require a careful assessment of the abnormal result within the clinical context on a case-bycase basis and will depend on the Investigator's medical judgment.

Abnormal laboratory test results detected after the screening visit whose CTCAE grades are 2 or higher or still are CTCAE grade 1 and deemed clinically significant must be either recorded as AEs (and handled according to the directions in Section 8.2) or linked to a concomitant disease or still to an already reported AE.

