# 11.2 Data Handling

All study data will be managed by the Data Management Team at the CRO. The overall procedures for quality assurance of clinical study data are described in the SOPs of the CRO Data Management Team. The Data Management Team at CRO will prepare a DMP, to be reviewed and approved by the Sponsor, prior to the start of the study. This document will describe, in detail, the Data Management related procedures and processes.

All data of all subjects enrolled and screening failures who experience an AE during the study (from time of informed consent) will be captured. All data collected during the study is property of the Sponsor irrespective of the location of the database and the Data Management CRO.

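### As titled, no AE output in the SAP would show an adverse event in a screening failure, although the protocol captures such events

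*SAP*

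**What the plan says.** Protocol 8.2.2 gives the collection period and names no population: "AEs (including SAEs) will be collected from the time of ICF signature until the EOS". It goes on: "Any AEs which occur during the screening period will be captured by the study site staff", so that their relationship to study procedures can be judged. Protocol 11.2 names subjects who were never enrolled: "All data of all subjects enrolled and screening failures who experience an AE during the study (from time of informed consent) will be captured".

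SAP 9.6.4.1 repeats the 8.2.2 sentence with four words added at the end: "AEs (including SAEs) will be collected from the time of ICF signature until the EOS for all enrolled subjects". A later sentence in the same section says that screening-period events will be listed, again without naming a population.

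SAP 13.2 does name one. Listings 15.3.7.1 (pre-treatment AEs), 15.3.7.2 (all AEs) and 15.3.7.3 (deaths and other SAEs) are all titled for the Safety Set. Protocol 12.4.3 and SAP 8.2 define that set as enrolled subjects with a signed ICF and at least one valid safety assessment. The protocol's Explanation of Terms makes a screening failure, by definition, someone who was not enrolled.

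**The concern.** The protocol gathers adverse events in people who consent and then fail screening. The SAP describes a narrower scope and plans no AE output that would display those events.

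This matters because V1 is not a paper visit. It includes spirometry with salbutamol and an exercise test to volitional fatigue. Protocol 2.3.2 lists, among the risks of that test, "light headedness, fatigue, and in rare instances, heart attack". The protocol also foresees adverse events in people who never enrol. Under 8.4.1, "Subjects with clinically significant abnormal laboratory values at Screening will not be enrolled", and such results, although usually a sign of concomitant disease, can in some cases be assessed as AEs.

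At stake is the completeness of the safety account under objective 11. An event that followed a study procedure at V1 could sit in the database and yet be missing from the planned AE outputs for the study report.

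**Working it through.** There is no planned figure to reproduce, so the check sets the texts side by side and traces the populations.

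1. **Collection wording.** Protocol 8.2.2 runs from ICF signature to EOS with no population. SAP 9.6.4.1 has the same sentence, limited to enrolled subjects. Protocol 11.2 explicitly includes screening failures with an AE. On this sentence the SAP is narrower than the protocol.

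2. **Who is outside the Safety Set.** Screening failures are not enrolled (Explanation of Terms), and the Safety Set requires enrolment (protocol 12.4.3, SAP 8.2). No screening failure can be in it.

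3. **Timing.** Spirometry and the VO2max test are at V1 (protocol 9.1, Table 5). Enrolment is at V2, after the cotinine, exhaled CO, alcohol, drug and pregnancy checks (protocol 9.2, Table 6). A subject can therefore complete the maximal test and fail afterwards, for example on the VO2max limits in exclusion criterion 7 or on a V2 check.

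4. **Population of each AE output in SAP 13.2.**
   - AE tables 15.2.3.1.1 to 15.2.3.1.9: 9, all on the Safety Set.
   - AE listings 15.3.7.1 to 15.3.7.3: 3, all on the Safety Set.
   - Total: 9 + 3 = 12 on the Safety Set, and 0 on screened subjects.
   - Outputs that are titled for screened subjects cover disposition, enrolment and product preference (Table 15.2.1.1; Listings 15.3.1.2, 15.3.1.3, 15.3.4.2). None is an AE output.

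5. **Result.** An AE in a screening failure is captured (protocol 11.2), but as titled it appears in none of the 12 outputs.

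6. **What would need to change.** A screening failure never receives a product allocation, so every AE in such a subject is pre-treatment and belongs in Listing 15.3.7.1. A death or other SAE also belongs in 15.3.7.3. That is 2 of the 12 outputs. The tables are by study arm and a screening failure has no arm, so they need no change.

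7. **Size.** Neither document gives the number of screening failures or of AEs among them, so the number of affected subjects cannot be calculated.

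**The case against.** The case on the other side is substantial, and much of it stands.

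- **The SAP does not govern collection.** Protocol 8.2.2 and 11.2 do. A reader might infer that AEs in screening failures will not be collected. The documents do not support that: the SAP line is descriptive, and the protocol requires capture.
- **The enrolled-only Safety Set is the protocol's own.** A reader might infer that the SAP changed the safety population without declaring it in SAP 7. It did not. That section covers changes to protocol-specified analyses, and protocol 12.4 already places safety on this set. Only the collection wording differs.
- **No promise is broken.** The protocol says that these data are captured. It does not say that they will be listed.
- **The SAP sentence on listing screening-period events could be read to include screening failures.** This is possible, but the one matching output, Listing 15.3.7.1, is titled for the Safety Set. The detailed shells are in a separate document (SAP 1). The title of Listing 15.3.4.3 cannot be read, and Table 15.2.3.1.10 is absent from the list. Neither is shown to be an AE output, but the conclusion should be limited to the outputs as titled.
- **Selective omission.** Because one exclusion criterion is "Inability to perform a VO₂max test at V1", a reader might infer that an AE which stops the test turns the subject into a screening failure, so that harms of the test are lost preferentially. The documents do not say that an AE triggers this criterion. Protocol 9.1 also allows the test only after the clinical assessments and a judgement that the subject is healthy.
- **EOS has no meaning for a screening failure.** It is tied to V44 or early termination, and only enrolled subjects can be discontinued (protocol 5.2). This is a fair defence of the four added words, but the protocol's own sentence has the same looseness, and matching it is the simpler course.

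**Conclusion.** The point holds as a minor reporting gap. The SAP's collection sentence is narrower than the protocol's, and all 12 AE outputs with readable titles are on a set that excludes screening failures. An AE, SAE or death after a V1 procedure in a subject who then fails screening would be captured but, as titled, not shown in any planned AE output.

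The number of such events is unknown and may be zero. The by-arm AE tables, the endpoints and the 24-hour SAE reporting under protocol 8.3 are unaffected.

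The conclusion assumes that the listings will be produced on the populations in their titles. It does not rest on any estimate of the screening-failure or event rate, and it does not claim that collection stops, that the safety population was altered, or that the omission favours any kind of event.

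**What to change.** 1. In SAP 9.6.4.1, delete the last four words of the collection sentence so that it agrees with protocol 8.2.2. Do not add an end date for screening failures. The protocol sets none, and a cut-off at the time of screening failure could drop a delayed reaction to a V1 procedure.
2. Produce Listings 15.3.7.1 and 15.3.7.3 on all screened subjects with a signed ICF, and flag the screening failures.
3. Leave the Safety Set definition, Listing 15.3.7.2 and all AE tables as they are.

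No new data are needed, since protocol 11.2 already captures them, and SAP 13.2 already uses a screened-subjects population. Item 2 changes the population as well as the title, so the shells and programs for two listings need a small edit. If the change comes after the SAP is final, it is described in the study report, as SAP 1 provides. The only downside is slightly longer listings.

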9.6.4.1.1 Serious Adverse Events (Including Deaths)

The frequency of SAEs will be determined within each study arm and for all study arms (total). Furthermore, the absolute and relative frequencies for subjects with a given SAE with respect to the system organ class (SOC) and preferred term according to MedDRA® will be determined within each study arm and for all study arms (total) and tabulated. Tabulation will be sorted by the decreasing frequencies within the system organ classes and preferred term (within the system organ class).

Data and information contained in this document are considered to constitute trade secrets and confidential commercial information, and the legal protections provided to such trade secrets and confidential information are hereby claimed under the provisions of applicable law. No part of this document may be publicly disclosed without the written consent of Philip Morris Products S.A

Philip Morris Products SA.	Statistical Analysis Plan	Confidential
P1-EXC-01-EU	Final 2.0	Page 54 of 71
Related to PMI-RRP-WKI-112487		GAD DI EVO 01 EU

9.6.4.1.2 Adverse Events Leading to Discontinuation

The frequency of AEs/SAEs leading to the subject's withdrawal from the study will be determined within each study arm and for all study arms (total) and summarized.

9.6.4.2 Device Events

All IQOS device issues and/or malfunctions will be listed, including event description, severity of event, AE relationship, proposed solution and start/stop dates/times.

The frequency of device events will be determined within each study arm and for all study arms (total). Furthermore, the absolute and relative frequencies for subjects with a given device event with respect to the system device event term will be determined within each study arm and for all study arms (total) and tabulated.

The frequencies of the severity (intensity) and relationship to study procedures for each device events will be tabulated for each study arm by device event term.

A summary table of AEs related and expected to device events will be presented as well.

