## 6.6.2 Storage and Accountability

The Investigator or a designated study collaborator will be responsible for the storage and accountability of the *IQOS* devices and HeatSticks to be distributed only once at V3, together with the device. The *IQOS* devices (charger and holder) as well as HeatSticks (to be distributed only once at V3, together with the device) will be stored in a secured storage site with access limited to authorized personnel only.

A sufficient number of *IQOS* starter kit will be stored at site, to be delivered to subjects allocated to the two *IQOS* arms only. A few additional devices will be stored in case a subject needs to have his/her *IQOS* device replaced. Full accountability of the distributed *IQOS* starter kit and replacement devices, if any, will be ensured by the designated study collaborator and recorded in IP accountability logs. This includes but is not limited to the record of the device serial number, HeatSticks batch number, the quantity of devices and HeatStick packs delivered per subject, date of delivery, total quantity available at site, the quantity of devices returned to the site at the end of the study.

Except for the initial packs of HeatSticks delivered within the *IQOS* starter kit at V3, neither HeatSticks nor cigarettes will be stored at site during the study as they will be bought by the subjects throughout the study.

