- 9. To monitor levels of exposure to CO, nitrosamines and acrylonitrile in subjects switching to IQOS (with and without training), continuing to smoke cigarettes (with training) and being smoking abstinent (with training)

Endpoints

At all visits:

• Exhaled carbon monoxide (CO) (ppm)

At V3, V4, V14, V28 and V43

- Carboxyhemoglobin (COHb%) in blood (%)
- Nicotine equivalents (NEQ) in urine (adjusted for creatinine)
- Total 4-(methylnitrosamino)-1-(3-pyridyl)-1-butanol (NNAL) in urine (adjusted for creatinine)
- 2-cyanoethylmercapturic acid (CEMA) in urine (adjusted for creatinine)

Confidentiality Statement

Philip Morris Products SA.	Statistical Analysis Plan	Confidential
P1-EXC-01-EU	Final 2.0	Page 11 of 71
Related to PMI-RRP-WKI-112487		

10. To describe the self-reported nicotine and tobacco containing product use over the duration of the study

Endpoints (measured daily from V2 to V43)

- Self-reported number of any nicotine/tobacco product use on a daily basis as reported in the product use diary
- Product use exposure
- 11. To monitor safety during the study

Endpoints

- Incidence of adverse events (AEs), serious adverse events (SAEs)
- Frequency of AEs, SAEs
- Incidence of IQOS device events including malfunction/misuse
- Frequency of IQOS device events including malfunction/misuse
- Vital signs changes from baseline (systolic and diastolic blood pressure, pulse rate and respiratory rate)
- Physical examination changes from baseline
- Electrocardiogram (ECG) changes from baseline (heart rate, PR, QRS, QT, QTcB, QTcF intervals)
- Spirometry changes from screening visit (V1) used as baseline (FEV1, FEV1 % predicted, FVC, FVC % predicted, and FEV1/FVC)
- Cough assessment changes from baseline (VAS and three Likert scales)
- Changes from baseline in clinical chemistry, hematology, and urine analysis safety panel
- Concomitant medications
- 12. To assess perception of health and functioning in subjects switching to IQOS, continuing to smoke cigarettes and being smoking abstinent **

Endpoints (first interview between V2 and V3, second interview between V42 and V43)

• Changes in subjects' perception of health and functioning as determined by qualitative interviews based on the World Health Organization's International Classification of Functioning, Disability, and Health

** This objective will be assessed as a sub-study with a separate section of the Informed Consent Form (ICF), and the reporting will be subject of an appendix to the main CSR.

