4 INVESTIGATIONAL PLAN

4.1 Study Design

This is a randomized, controlled, open-label, 4-arm parallel group study with stratification by daily cigarette consumption over the past 12 months prior to V1 as reported during V1 (i.e. 10 to 19 cigarettes or >19 cigarettes per day) and sex (Figure 1).

A sufficient number of healthy adult smokers will be screened and enrolled after checking that all eligibility criteria have been met, in order to reach 90 randomized subjects.

Smokers will be randomized as follows with a 5:5:5:3 ratio according to strata:

- **1.** switch to IQOS use + participation in training program: IQOS-1 arm, 25 subjects
- **2.** continue cigarette smoking + participation in training program: Cigarette arm, 25 subjects
- **3.** smoking abstinence + participation in training program: SA arm, 25 subjects
- **4.** switch to IQOS use only: IQOS-2 arm, 15 subjects

When 90 randomized subjects are reached, further enrollment will be stopped. Subjects already enrolled in the study will still be eligible for randomization. From randomization, subjects will be instructed to use their allocated product or stay smoking abstinent until the end of the study. Drop-outs will not be replaced.

Acute effect on VO2max and exercise capacity of switching to IQOS will be assessed one week after randomization before initiating the training program, and the combined effect of switching and exercise training will be assessed one week after completion of the 12-week training program.

Figure 1 Study Design

Confidentiality Statement

Philip Morris Products SA.	Statistical Analysis Plan	Confidential
P1-EXC-01-EU	Final 2.0	Page 14 of 71
Related to PMI-RRP-WKI-112487		SAP P1-EXC-01-EU

Subjects will have serial visits at the investigational site as follows:

Screening, V1 (within 28 days prior to V2): No study-specific procedures will be performed before the Informed Consent Form (ICF) has been signed. The subject will also be invited to participate in a sub-study on perception of health and functioning and will sign a separate optional section of the ICF for this part of the study. Subjects will be invited to sign a separate optional consent form for collection of samples for biobanking.

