8.2 Safety Set

The Safety Set consists of all subjects enrolled with signed ICF who have at least one valid safety assessment during the course of the study. The Safety Set will be analyzed by actual exposure (product use exposure, actual study arm).

Confidentiality Statement

Philip Morris Products SA.	Statistical Analysis Plan	Confidential
P1-EXC-01-EU	Final 2.0	Page 31 of 71
Related to PMI-RRP-WKI-112487		SAD DI EVC OI EU

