Table 15.2.3.1.1: Overview of Adverse Events – Safety Set	X
Table 15.2.3.1.2: Summary of Adverse Events by System Organ Class and	
Preferred Term – Safety Set	X
Table 15.2.3.1.3: Summary of Adverse Events Related to Investigational	
Product and Expectedness, System Organ Class and Preferred Term - Safety Set	X
Table 15.2.3.1.4: Summary of Adverse Events by Severity, System Organ Class	
and Preferred Term - Safety Set	

Confidentiality Statement

Philip Morris Products SA.	Statistical Analysis Plan	Confidential
P1-EXC-01-EU	Pending Approval 0.1, CURRENT, IN PROGRESS	Page 69 of 71
Related to PMI-RRP-WKI-112487		DD SME01 810208 SAD D1

Table 15.2.3.1.5: Summary of Adverse Events Leading to Product	X
Discontinuation, Interruption or Reduction by System Organ Class and Preferred Term – Safety Set	X
Table 15.2.3.1.6: Summary of Adverse Events Leading to Study Discontinuation	X
by System Organ Class and Preferred Term – Safety Set	X
Table 15.2.3.1.7: Summary of Serious Adverse Events by System Organ Class	
and Preferred Term – Safety Set	
Table 15.2.3.1.8: Summary of Adverse Events related to Study Procedure by	
System Organ Class and Preferred Term – Safety Set	
Table 15.2.3.1.9: Summary of Frequent Adverse Events (Incidence >5%) by	
System Organ Class and Preferred Term – Safety Set	
Table 15.2.3.1.11: Summary of Device Events and Malfunctions - Safety Set	Х
Table 15.2.3.1.12: Summary of Medical History by System Organ Class and	
Preferred Term – Safety Set	
Table 15.2.3.1.13: Concomitant Medications by ATC and Preferred Drug Name	x
– Safety Set	^
Table 15.2.3.1.14: Concomitant Diseases by System Organ Class and Preferred	
Term – Safety Set	
Table 15.2.3.1.15: Prior Medications by ATC and Preferred Drug Name – Safety	x
Set	~
Table 15.2.3.2.1: Summary of Hematology Parameters by Product Use	
Category – Safety Set	
Table 15.2.3.2.2: Summary of Clinical Chemistry Parameters by Product Use	
Category – Safety Set	
Table 15.2.3.2.3: Summary of Urinalysis Parameters by Product Use Category –	
Safety Set	
Table 15.2.3.4.1: Summary of Vital Signs by Product Use Category – Safety Set	X
Table 15.2.3.4.2: Descriptive Statistics of ECG – Safety Set	X
Table 15.2.3.4.3: Descriptive Statistics of Spirometry at Screening, Discharge or	x
Early Termination – Safety Set	
Table 15.2.3.4.4: Summary of Physical Examination – Safety Set	X
Table 15.2.3.4.5: Summary of Cough-VAS and Likert Scales – Safety Set	Х

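### The all-arms percentage of subjects with a device event has no restriction to device holders, so at planned numbers it would show about 44% of the incidence among those issued a device

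*SAP*

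**What the plan says.** SAP 3.1 (objective 11) names "Incidence of IQOS device events including malfunction/misuse" as a safety endpoint, alongside the frequency of such events.

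SAP 9.6.4.2 plans two summaries with the same columns. The first is a count of events: "The frequency of device events will be determined within each study arm and for all study arms (total"). The second is at subject level: "the absolute and relative frequencies for subjects with a given device event with respect to the system device event term", again by arm and for all arms together. The SAP does not state the denominator of the relative frequencies.

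The output is "Table 15.2.3.1.11: Summary of Device Events and Malfunctions - Safety Set". SAP 8.2 defines that set without reference to randomisation or to holding a device: "The Safety Set consists of all subjects enrolled with signed ICF who have at least one valid safety assessment". It adds: "The Safety Set will be analyzed by actual exposure (product use exposure, actual study arm"). SAP 9.1.1 gives the use groups as Cigarette, IQOS-1, SA, IQOS-2, Dual-1 and Dual-2.

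Protocol 6.6.2 has starter kits stored at the site, "to be delivered to subjects allocated to the two *IQOS* arms only". Protocol 6.6.1 allows for a subject buying a device of their own.

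**The concern.** A device can malfunction or be misused only in the hands of someone who has one. A percentage taken over all arms puts in its denominator the cigarette and SA subjects, to whom the study issues no device. The resulting figure is not the incidence of device events among those exposed to the risk.

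The wording closely follows the serious adverse event paragraph (SAP 9.6.4.1.1): same sentence order, same total column. An all-subjects denominator suits serious adverse events, where everyone is at risk. It does not suit device events.

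The by-arm columns only partly repair this, because they are use groups and not randomised arms. A holder who goes back mainly to cigarettes can leave the IQOS columns. A holder with more than half of the diary data missing becomes 'Others' (SAP 5.5.1), and SAP 9.4 says that group is only listed. The number of subjects issued a device therefore need not appear anywhere in the table.

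At stake is a named safety endpoint for the sponsor's product. The dilution makes the device look more reliable. Holders who gave up the product, possibly because of a fault, are among those whom the grouping can move.

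**Working it through.** **Inputs**
- SAP 4.1: 90 randomised. "Smokers will be randomized as follows with a 5:5:5:3 ratio according to strata", with IQOS-1 25, Cigarette 25, SA 25, IQOS-2 15.
- Protocol 6.6.2: study devices go to IQOS-1 and IQOS-2 only.
- The documents state no expected device-event incidence, so the event numbers below are illustrations.

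**Step 1: reproduce the plan's allocation.** 90 × 5/18 = 25 for three arms and 90 × 3/18 = 15 for IQOS-2. This matches.

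**Step 2: holders and non-holders.** Issued a device: 25 + 15 = 40. Not issued one: 25 + 25 = 50.

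**Step 3: dilution.** With *k* subjects affected, all of them holders, the total column prints *k*/90, while the incidence among holders is *k*/40. The ratio is 40/90 = 0.444 whatever *k* is: a relative understatement of 1 − 0.444 = 55.6%, or a factor of 90/40 = 2.25.

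| Subjects with an event | Among 40 holders | Total column (of 90) |
|---|---|---|
| 4 | 10.0% | 4.4% |
| 8 | 20.0% | 8.9% |
| 12 | 30.0% | 13.3% |

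**Step 4: how far the ratio moves.** The first column is assumed; the documents give no such numbers.

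| Departure from the planned split | Ratio | Understatement |
|---|---|---|
| 5 cigarette/SA subjects have their own device | 45/90 = 0.50 | 50.0% |
| 10 cigarette/SA subjects have their own device | 50/90 = 0.56 | 44.4% |
| 10 non-holders leave the denominator as 'Others' | 40/80 = 0.50 | 50.0% |
| 15 non-holders leave as 'Others' | 40/75 = 0.53 | 46.7% |
| 5 holders leave as 'Others' | 35/85 = 0.41 | 58.8% |
| 10 holders leave as 'Others' | 30/80 = 0.375 | 62.5% |

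In the last two rows the comparison is with the incidence among the holders who remain. Across all these cases the total column understates by roughly 44% to 63%.

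**Step 5: what is not affected.** Event counts have no denominator and are not diluted. SAP 13.2 also plans Listing 15.3.10.2 (device events) and Listing 15.3.10.3 (device accountability).

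**The case against.** The strongest reply is that the denominator is inferred. SAP 9.6.4.2 does not state it, and SAP 1 leaves the detailed table layout to a separate shell document that is not available here. That document may restrict it. This stands as a limit, but the SAP text, the Safety Set title and the all-arms total point one way, and no section points the other.

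Second, per-holder incidence is not lost. The two listings cover at most about 40 holders of study devices, and SAP 9.1.1 says data are listed by randomised arm, so a reader could count. This also stands. A reader might infer that the incidence cannot be recovered at all. It cannot be read from the summary table, but it can be worked out from the listings.

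Third, a reader might infer that at least 50 subjects could never have an event, and so that the figure is always more than half too low. The documents do not support either as a certainty. Protocol 6.6.1 foresees own devices, Protocol 12.3 expects some IQOS use outside the IQOS arms, and 'Others' may leave the denominator.

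Fourth, one might add that enrolled but unrandomised subjects lower the percentage further. They can belong to the Safety Set, but the total is over study arms, they have no arm, and product use is categorised only from V3. Nothing shows that they enter this total.

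Fifth, the extent of regrouping cannot be judged. The cut-offs are in SAP Figure 2, which is not reproduced in the available text, and Dual-1 and Dual-2 would keep many mixed users out of the Cigarette column. The treatment of 'Others' in safety tables is also not fully settled: SAP 9.4 has them listed only, while SAP 9.6.1.2 presents them descriptively, but for non-safety endpoints.

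**Conclusion.** The point holds. As written, SAP 9.6.4.2 and Table 15.2.3.1.11 give an all-arms percentage of subjects with a device event that is not an incidence among device holders. At the planned 40 of 90 it would be about 44% of that incidence. This rests on three assumptions: the denominator is everyone in the arms, no cigarette or SA subject has a device, and few subjects fall into 'Others'. The use-group columns do not fully make good the loss, because holders can be moved between columns or left out of the table.

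The practical weight is moderate. The study is descriptive, no decision rule uses this percentage, and counts and listings are sound. But the endpoint is named, the direction of the distortion is predictable and the correction is simple, so it should be made.

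**What to change.** In SAP 9.6.4.2 and the shell for Table 15.2.3.1.11:

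- State the denominator: subjects issued a study IQOS device.
- Show IQOS-1 and IQOS-2 as randomised, plus their sum.
- Report any own-device users separately.
- Drop the all-arms total percentage.

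The cost is one paragraph and one table shell. Device accountability is already to be listed, so the main change needs no new data. The downside is a less favourable percentage and one safety table that departs from the Safety Set grouping; a footnote can explain why.

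A rate per device-days is optional. The accountability log in Protocol 6.6.2 names the date of delivery but, for returns, only the quantity. The end of exposure would therefore have to come from the V43 or early-termination visit date, using the return rule in Protocol 6.6.3 and Listing 15.3.10.5.
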